10.4.1.1. Treatment States for AE Data

Treatment State	Definition
Onset Time Since 1 st Dose (Days)	If Treatment Start Date > AE Onset Date = AE Onset Date - Treatment Start Date If Treatment Start Date ≤ AE Onset Date = AE Onset Date - Treatment Start Date + 1 Missing otherwise.
Duration (Days)	AE Resolution Date – AE Onset Date + 1
Drug-related	If relationship is marked 'YES' on eCRF OR value is missing.
Onset before Day 7	AE Start Date ≤ Study Day 7
Onset on days 8-15	Study Day 8 ≤ AE Start Date < Study Day 16
Onset on days 16-29	Study Day 16 ≤ AE Start Date < Study Day 30
Onset in Months 2 or 3	Study Day 30 ≤ AE Start Date < Study Day 91
Onset after Month 3	AE Start Date ≥ Study Day 91

10.5. Appendix 5: Data Display Standards & Handling Conventions

10.5.1. Study Treatment & Sub-group Display Descriptors

Treatment Group Descriptions			
Data Displays for Reporting			
Description	Description – Interim 1	Description – Interim 2 and Final	Order ^[1]
≥ 5 kg to ≤ 10 kg		TQ 50mg	1
> 10 kg to ≤ 20 kg ^[2]		TQ 100mg	2
> 10 kg to ≤ 20 kg ^[3]	TQ 150mg	TQ 150mg	3
> 20 kg to ≤ 35 kg	TQ 200mg	TQ 200mg	4
> 35 kg	TQ 300mg	TQ 300mg	5
Tafenoquine	Total	Total	6

NOTES:

1. Order represents treatments being presented in TFL, as appropriate.
2. Subjects from Cohorts 2 and 3
3. Subjects from Cohort 1

10.5.2. Baseline Definition & Derivations

10.5.2.1. Baseline Definitions

For all endpoints the baseline value will be the latest pre-Tafenoquine dose assessment on Day 1.

Asexual parasite and gametocyte counts

If there are multiple pre-treatment assessments, a subject will be considered to have a positive (non-zero) baseline assessment if *any* of the assessments are positive. They will only be considered to have a zero baseline count if all of the pre-treatment assessments are slide negative.

10.5.2.2. Derivations and Handling of Missing Baseline Data

Definition	Reporting Details
Change from Baseline	= Post-Dose Visit Value – Baseline
% Change from Baseline	= 100 x [(Post-Dose Visit Value – Baseline) / Baseline]

NOTES:

- Unless otherwise specified, the baseline definitions specified in Section 10.5.2 Baseline Definitions will be used for derivations for endpoints / parameters and indicated on summaries and listings.
- Unless otherwise stated, if baseline data is missing no derivation will be performed and will be set to missing.
- The baseline definition will be footnoted on all change from baseline displays.

10.5.3. Reporting Process & Standards

Reporting Process	
Software	

 The currently supported versions of SAS software will be used. 	
Reporting Area	
HARP Server	: UK1SALX00175
HARP Area	: /arenv/arprod/sb252263/taf113577/internal_01 : /arenv/arprod/sb252263/taf113577/internal_02 /arenv/arprod/sb252263/taf113577/final_01
QC Spreadsheet	: /arenv/arprod/sb252263/taf113577/final_01/qc
Analysis Datasets	

 Interim analysis datasets will be created according to legacy GSK IDSL A&R dataset standards. Final analysis datasets will be created according to CDISC standards (SDTM IG Version 3.1.3 & AdaM IG Version 1.0). For creation of ADaM datasets (ADCM, ADC1 and ADAE), the same version of dictionary datasets will be implemented for conversion from SI to SDTM. 	
Generation of RTF Files	

 RTF files will be generated for interim and final analyses. 	

Reporting Standards	
General	

 The current GSK Integrated Data Standards Library (IDSL) will be applied for reporting, unless otherwise stated: 
 4.03 to 4.23: General Principles 5.01 to 5.08: Principles Related to Data Listings 6.01 to 6.11: Principles Related to Summary Tables 7.01 to 7.13: Principles Related to Graphics 	
Formats	

 All data will be reported according to the actual treatment the subject received unless otherwise stated. GSK IDSL Statistical Principles (5.03 & 6.06.3) for decimal places (DP's) will be adopted for reporting of data based on the raw data collected. Numeric data will be reported at the precision collected on the eCRF. The reported precision from non eCRF sources will follow the IDSL statistical principles but may be adjusted to a clinically interpretable number of DP's. 	
Planned and Actual Time	

 Reporting for tables, figures and formal statistical analyses: 
 Planned time relative to dosing will be used in figures, summaries, statistical analyses and calculation of any derived parameters, unless otherwise stated. The impact of any major deviation from the planned assessment times and/or scheduled visit days on the analyses and interpretation of the results will be assessed as appropriate. 	

Reporting Standards	

 • Reporting for Data Listings: 
 • Planned and actual time relative to study drug dosing will be shown in listings (Refer to IDSL Statistical Principle 5.05.1). • Unscheduled or unplanned readings will be presented within the subject's listings. • Visits outside the protocol defined time-windows (i.e. recorded as protocol deviations) will be included in listings. 	
Unscheduled Visits	

 • Unscheduled visits will not be included in summary tables, unless slotted to a scheduled visit (Section 10.3.1). The exception is when maximum/minimum values/changes post baseline are summarised, in which case, all data will be considered. • Unscheduled visits will not be included in figures, unless slotted to a scheduled visit (Section 10.3.1). The exception is when maximum/minimum values/changes post baseline are plotted, in which case, all data will be considered. • All unscheduled visits will be included in listings. 	
Descriptive Summary Statistics	
Continuous Data	Refer to IDSL Statistical Principle 6.06.1
Categorical Data	N, n, frequency, %
Graphical Displays	

 • Refer to IDSL Statistical Principals 7.01 to 7.13. 	

10.6. Appendix 6: Derived and Transformed Data

10.6.1. General

Multiple Measurements at One Time Point

 If there are multiple assessments within the same window which are not unscheduled visits, the earliest results will be used in the summaries. All values will be listed. Subjects having both High and Low values for Normal Ranges at any post-baseline visits for safety parameters will be counted in both the High and Low categories of “Any visit post-baseline” row of related summary tables. This will also be applicable to relevant Potential Clinical Importance summary tables.
Study Day

 Study Day 1 is defined as the day the dose of study medication was taken. Study Day >1 calculated as the number of days from study Day 1 date: 
 Ref Date = Missing → Study Day = Missing Ref Date < Study Day 1 date → Study Day = Ref Date – study Day 1 date Ref Date ≥ Study Day 1 date → Study Day = Ref Date – (study Day 1 date) + 1
Cohort

 A subject’s cohort can be determined based on the date of study medication as follows: 
 Cohort 1 – Date of study medication <05-Jan-2018 Cohort 2 – Date of study medication ≥05-Jan-2018 and <26-Feb-2019 Cohort 3 – Date of study medication ≥26-Feb-2019

10.6.2. Study Population

Demographics
Body Mass Index (BMI)

 Calculated as Weight (kg) / [Height (m)]²
Prior and Concomitant Medications

 Medications will be coded using the latest version of GSK Drug. Prior medications = medications taken up to 30 days before the date and time of the first dose of study medication. Any medications with stop dates earlier than 30 days will not be reported in tables and listings. Concomitant medications = medications with start date and time on or after the start date and time of the dose of study medication (Study Day 1). Medications, with the exception of chloroquine, taken prior to the study and continuing during the study will be summarised as both prior medications and concomitant medications. All subjects were expected to take chloroquine prior to the start of study medication, and often continuing after the start date of study medication. The number and percent of subjects taking prior chloroquine will be summarised separately to other prior medications. If chloroquine treatment is started after the start of study medication, e.g. to treat a relapse, this should be reported in the same way as other concomitant medications. All chloroquine data (prior and

Prior and Concomitant Medications

concomitant) will be included in the listing of prior and concomitant medications.

- See Section 10.7.2 for the handling of missing and partial dates.

Treatment Compliance and Exposure

- All study medication will be administered at the investigator centre in the presence of the Investigator or study nurse, and ingestion confirmed.
- On the day of dosing, a subject will be classified as compliant with daily administered dose if they do not vomit the initial dose or if they are successfully re-dosed.
- A subject is considered to be compliant in clinic if they retain all study medication given to them.
- Subjects who were entered but did not report a treatment start date will be categorised as having zero doses.
- Study treatment consists of a single dose so duration of exposure will not be calculated.

G6PD enzyme activity as a percentage of site median

- Each site has a median G6PD enzyme value for healthy G6PD-normal subjects, determined from G6PD-normal males in study TAF115226:

Region	Country	Site	Investigator	Centre ID	G6PD median value (IU/g Hb)
South America	Brazil	Fundação de Medicina Tropical do Amazonas, Amazonas	[name]	PPD	7.92
	Colombia	Oncomedica SA, Monteria	[name]	PPD	8.32
	Peru	Asociacion Civil Selva Amazonica, Iquitos	[name]	PPD	9.01
Asia	Thailand	Mea Sot General Hospital, Tak	[name]	PPD	7.79
	Thailand	Hospital for Tropical Disease, Bangkok	[name]	PPD	7.40
	Vietnam	National Institute of Malariology, parasitology and entomology (NIMPE), Hanoi	[name]	PPD	10.51
	Vietnam	Oxford University Clinical Research Unit, Ho Chi Minh City	[name]	PPD	8.38

G6PD enzyme activity as a percentage of site median						
		Vietnam	OUCRU-Phuoc Long Medical Center, Ho Chi Minh City	[name]	PPD	8.38

- Enzyme activity as percentage of site median = (absolute enzyme activity / site median) x 100%
- G6PD deficient subjects are defined as those with a G6PD enzyme activity <70% of the site median.

10.6.3. Safety

Adverse Events

 • All AEs reported up to and including the Day 120 visit following enrolment of a subject into the study will be documented. • These will be recorded and coded using the current version of Medical Dictionary for Regulatory Activities (MedDRA). All terms applied will be reviewed by a GSK physician prior to database freeze. If any malaria related coded terms are considered to have lost useful information in the coding step (e.g., if a verbatim term of 'Plasmodium vivax malaria' is mapped to 'malaria'), he/she will recommend a study-specific code, which will be documented. • Treatment emergent AEs are defined as AEs with an onset date and time on or after that of the start of first dose of study medication (including CQ). • AEs with entirely missing or unknown start dates will be assumed to be treatment emergent for reporting. AEs where the start date is equal to that of study medication, but where the start time is unknown will also be assumed to be treatment emergent. AEs with missing end dates are not anticipated to affect reporting. • If the grade/intensity is missing for an AE, it will be considered severe/Grade 3 if an AE, or Grade 4 if an SAE and the subject is alive, or Grade 5 if an SAE and the subject dies (i.e. the highest intensity possible) for the summary of AEs by maximum intensity. • See Section 10.7.2 for more information on missing and partial dates. • Common AEs are those occurring in ≥10% of subjects in any treatment group. • The recurrence of malaria and any associated signs and symptoms are recorded as Disease Related Events (DREs) and will not be classified as AEs. • The GSK clinical team will review terms that qualify as potentially hematologically related.

Laboratory Parameters

 • If a laboratory value which is expected to have a numeric value for summary purposes, has a non-detectable level reported in the database, where the numeric value is missing, but typically a character value starting with '<x' or '>x' is present, the number of decimal places of x will be used to determine how much to add or subtract in order to impute the corresponding numeric

Laboratory Parameters

value.

- Example 1: 2 decimal place = '< x' becomes $x - 0.01$
- Example 2: 1 decimal place = '> x' becomes $x + 0.1$
- Example 3: 0 decimal places = '< x' becomes $x - 1$

Vital Signs – Mean Arterial Blood Pressure

- To be calculated (to 1 decimal place) where systolic and diastolic blood pressure are both present at the same timepoint:

[figure not shown]
mean arterial blood pressure

$$= \frac{(\textit{systolic blood pressure} + 2(\textit{diastolic blood pressure}))}{3}$$

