12.3.5. Evaluating AEs and SAEs

Assessment of Intensity

The investigator will make an assessment of intensity for each AE and SAE reported during the study and will assign it to one of the following categories:

- Mild: An event that is easily tolerated by the subject, causing minimal discomfort and not interfering with everyday activities.
- Moderate: An event that is sufficiently discomforting to interfere with normal everyday activities
- Severe: An event that prevents normal everyday activities. - an AE that is assessed as severe will not be confused with an SAE. Severity is a category utilized for rating the intensity of an event; and both AEs and SAEs can be assessed as severe.
- An event is defined as 'serious' when it meets at least one of the pre-defined outcomes as described in the definition of an SAE.

Assessment of Causality

- The investigator is obligated to assess the relationship between study treatment and the occurrence of each AE/SAE.
- A "reasonable possibility" is meant to convey that there are facts/evidence or arguments to suggest a causal relationship, rather than a relationship cannot be ruled out.
- The investigator will use clinical judgment to determine the relationship.
- Alternative causes, such as natural history of the underlying diseases, concomitant therapy, other risk factors, and the temporal relationship of the event to the study treatment will be considered and investigated.
- The investigator will also consult the Investigator Brochure (IB) and/or Product Information, for marketed products, in the determination of his/her assessment.
- For each AE/SAE the investigator **must** document in the medical notes that he/she has reviewed the AE/SAE and has provided an assessment of causality.
- There may be situations when an SAE has occurred and the investigator has minimal information to include in the initial report to GSK. However, **it is very important that the investigator always make an assessment of causality for every event prior to the initial transmission of the SAE data to GSK.**
- The investigator may change his/her opinion of causality in light of follow-up

information, amending the SAE data collection tool accordingly.

- The causality assessment is one of the criteria used when determining regulatory reporting requirements.

Follow-up of AEs and SAEs

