10.15.6. Safety Tables

Safety: Tables						
No.	IA No.	Population	IDSL / Example Shell	Title	Programming Notes	Deliverable
Adverse Events (AEs)						
3.1.	3.1	Safety	AE1	Summary of All Treatment Emergent Adverse Events by System Organ Class and Preferred Term	ICH E3 Add footnote: 'Events are ordered based on Total incidence'. Please check data to determine how many subjects had events of vomiting occurring on day 1, and add a footnote to provide this information, e.g. "Of the X subjects with AEs of vomiting, Y experience vomiting on Day 1".	IA1, IA2, SAC
3.2.		Safety	AE3	Summary of Common Treatment Emergent Adverse Events ($\geq 10\%$ in Any Treatment Group) by Preferred Term	ICH E3, GSK CTR Order events in descending order.	SAC
3.3.		Safety	AE15	Summary of Common ($\geq 10\%$ in Any Treatment Group) Non-serious Treatment Emergent Adverse Events by System Organ Class and Preferred Term (Number of Subjects and Occurrences)	FDAAA, EudraCT	SAC

Safety: Tables						
No.	IA No.	Population	IDSL / Example Shell	Title	Programming Notes	Deliverable
3.4.	3.2	Safety	AE3	Summary of All Drug-Related Treatment Emergent Adverse Events by Preferred Term	GSK CTR Order events in descending order. Please check data to determine how many drug-related events of vomiting occurred on day 1, and add a footnote to provide this information, e.g. 'All drug-related AEs of vomiting occurred on day 1', or '9 of the 10 drug-related AEs of vomiting occurred on day 1'.	IA1, IA2, SAC
3.5.	3.3	Safety	AE5B	Summary of All Drug-related Treatment Emergent Adverse Events by System Organ Class and Maximum Grade or Intensity	The following AE grades should be displayed: 1, 2, 1+2, 3, 4, All Grades. Output should be displayed for all subjects combined only (not by dose group).	IA1, IA2, SAC
3.6.		Safety	AE5A	Summary of Treatment Emergent Adverse Events by Maximum Grade or Intensity	Add footnote: 'Events are ordered based on Total incidence'	SAC
3.7.		Safety	AE3	Summary of All Treatment Emergent Adverse Events by Preferred Term	Order events in descending order.	SAC
3.8.	3.4	Safety	AE3	Summary of Treatment Emergent Adverse Events with Onset on or Prior to Study Day 7	Add footnote: 'Events are ordered based on Total incidence'	IA1, IA2, SAC
3.9.	3.5	Safety	AE3	Summary of Treatment Emergent Adverse Events with Onset Date on Study Days 8-15	Add footnote: 'Events are ordered based on Total incidence'	IA1, IA2, SAC

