3.10.	3.6	Safety	AE3	Summary of Treatment Emergent Adverse Events with Onset on Study Days 16-29	Add footnote: 'Events are ordered based on Total incidence'	IA1, IA2, SAC
3.11.	3.7	Safety	AE3	Summary of Treatment Emergent Adverse Events with Onset Date in Month 2 or 3	Add footnote: 'Events are ordered based on Total incidence'	IA1, IA2, SAC

Safety: Tables						
No.	IA No.	Population	IDSL / Example Shell	Title	Programming Notes	Deliverable
3.12.	3.8	Safety	AE3	Summary of Treatment Emergent Adverse Events with Onset After Month 3	Add footnote: 'Events are ordered based on Total incidence'	IA1, IA2, SAC
Serious and Other Significant Adverse Events						
3.13.		Safety	AE3	Summary of Fatal Serious Treatment Emergent Adverse Events	GSK CTR Order events in descending order.	SAC
3.14.		Safety	AE1	Summary of Serious Treatment Emergent Adverse Events by System Organ Class	GSK CTR, IDSL Add footnote: 'Events are ordered based on Total incidence'	SAC
3.15.	3.9	Safety	AE3	Summary of Serious Treatment Emergent Adverse Events by Preferred Term	GSK CTR Order events in descending order.	IA1, IA2, SAC
3.16.		Safety	AE3	Summary of Drug-Related Treatment Emergent Serious Adverse Events by Preferred Term	GSK CTR Order events in descending order.	SAC
3.17.		Safety	AE3	Summary of Drug-Related Fatal Serious Treatment Emergent Adverse Events by Preferred Term	GSK CTR Order events in descending order.	SAC
3.18.		Safety	AE16	Summary of Serious Adverse Events by System Organ Class and Preferred Term (Number of Subjects and Occurrences)	FDA, EudraCT	SAC
3.19.		Safety	AE3	Summary of Treatment Emergent Adverse Events Leading to Withdrawal from the Study	IDSL Order events in descending order.	SAC
3.20.		Safety	AE1	Summary of Treatment Emergent Adverse Events Considered to be Potentially Hematologically-Related	Add footnote: 'Events are ordered based on Total incidence'	SAC
3.21.		Safety	AE3	Summary of Grade 3 and Grade 4 Treatment-Emergent Adverse Events by Preferred Term	Include Grade 3 and Grade 4 events only. Order events in descending order.	SAC

Safety: Tables						
No.	IA No.	Population	IDSL / Example Shell	Title	Programming Notes	Deliverable
Laboratory: Chemistry						
3.22.	3.10	Safety	SA11	Summary of Clinical Chemistry Data by Time		IA1, IA2, SAC
3.23.	3.11	Safety	SA12	Summary of Change from Baseline in Clinical Chemistry Data by Time	ICH E3	IA1, IA2, SAC

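### The SAP's adverse event grades do not match the protocol's mild/moderate/severe scale, and a blank SAE rating is imputed above the worst rating an investigator can give

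*SAP*

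**What the plan says.** Protocol 12.3.5 asks the investigator to judge the intensity of each AE and SAE, and the investigator "will assign it to one of the following categories". There are three:

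- "Mild: An event that is easily tolerated by the subject" (first part of the definition)
- "Moderate: An event that is sufficiently discomforting to interfere with normal everyday activities"
- "Severe: An event that prevents normal everyday activities"

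Nothing lies above severe. The same section warns against confusing severity with seriousness and adds that "both AEs and SAEs can be assessed as severe", so serious events use the same three levels.

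The SAP uses numbers. Section 10.6.3 gives the rule for a missing rating: "If the grade/intensity is missing for an AE, it will be considered severe/Grade 3 if an AE, or Grade 4 if an SAE". Grade 4 is for a child who is living; when the child has died, the SAE becomes Grade 5. The section describes this as the highest possible intensity and limits the rule to the maximum-intensity summary. In 10.15.6, the note for Table 3.5 (drug-related events by maximum grade or intensity) reads "The following AE grades should be displayed: 1, 2, 1+2, 3, 4, All Grades" and pools all subjects. Table 3.6 gives all treatment-emergent events by maximum grade or intensity. The note for Table 3.21 reads "Include Grade 3 and Grade 4 events only".

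**The concern.** The severity of adverse events is part of a named secondary safety endpoint (protocol section 3, SAP 2.2). A severity table should show what investigators recorded. Any imputation for blanks should be conservative within that scale.

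Here the imputation goes past the top of the scale, and it does so because the event is serious. Protocol 7.5.1.1 shows why this matters: a sufficient fall in hemoglobin is reportable as an SAE on the laboratory value alone, whatever the child's symptoms. Such an event with its intensity left blank would be shown as Grade 4. A life-threatening event rated severe would be shown as Grade 3.

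Table 3.5 is delivered at both interims as well as at the final analysis. SAP 3.1 says that the interim review may lead to stopping the study or changing doses.

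**Working it through.** No figure in the plan needs reproducing. The check is a comparison of scales, followed by the size of one blank.

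**1. Map the two scales.** The only link in either document is in SAP 10.6.3, which pairs severe with Grade 3.

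| Case | Protocol 12.3.5 | Grade under SAP 10.6.3 |
|---|---|---|
| Any AE or SAE rated severe | top of the scale | 3 |
| Non-serious AE, rating blank | no rating | 3 |
| SAE, rating blank, child alive | no rating | 4 |
| SAE, rating blank, child died | no rating | 5 |

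For a non-serious AE, the imputed value equals the worst observable rating, which is a sound conservative rule. For an SAE it exceeds that rating by one or two grades.

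**2. Look for another source of Grades 4 and 5.** Neither document gives grading criteria for adverse events. CTC AE is cited only in SAP 10.8.1, as a footnote to the laboratory flags for creatine kinase and creatinine. SAP 2.1, which lists departures from the protocol, covers analysis populations, the name of the efficacy endpoint and the parasite-clearance window. It does not mention a change of severity scale.

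**3. Follow the rule into the displays.**

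- Table 3.5: the rule applies. Grade 4 can be filled only by imputation. An imputed Grade 5 has no level of its own and could be counted only under All Grades.
- Table 3.6: the rule applies. The grade layout is not specified, and the shells are not in the document (SAP 10.16).
- Table 3.21: this lists Grade 3 and 4 events by preferred term and is not a maximum-intensity summary, so the rule does not apply. On the protocol scale its Grade 4 content is empty whatever happens in the trial.

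**4. Size of one blank SAE rating.** The share is 1/n, where n is the number of children in the display.

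- Table 3.5, pooled, at the target of 60 children: 1/60 = 1.7%. The event must also count as drug-related.
- Table 3.6, by dose group (SAP 8.2.1.1). Group sizes are not fixed in the documents. Sixty children over the five displayed groups average 60/5 = 12. Assuming 10-15 per group, the share is 1/15 = 6.7% to 1/10 = 10%.
- Range: the simulated weight distribution in protocol Appendix 9 puts 5%, 23%, 33% and 36% of children in the four treated bands, lightest first. Of 60 children, that is 3, 13.8, 19.8 and 21.6. One child is then 33%, 7.2%, 5.1% and 4.6% of the band. The 10-20 kg band is split between the 100 mg and 150 mg groups, so one child there would be more than 7.2%. SAP 10.10.1 allows small groups to be refined.

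**The case against.** The strongest objection is that the eCRF, cited in SAP section 1 as Version 1, is not among the documents. The SAP repeatedly writes grade or intensity as alternatives. This may be template wording, or it may mean that a numeric grade is collected. In the second case Grades 4 and 5 could be observed. A reader might therefore infer that Grades 4 and 5 can never be anything but imputed, and the documents do not support that without the qualification that the protocol scale is the one in use. The mismatch itself stands under either reading. If grades are collected, protocol 12.3.5 does not describe the data, no grading criteria are named, and Table 3.5 still has no place for Grade 5.

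A reader might also infer that imputed Grade 4 events would appear in Table 3.21. The limiting clause in SAP 10.6.3 rules that out. The problem there is the opposite: an empty Grade 4 part could be read as showing that no worse-than-severe event occurred, when the scale could not have recorded one.

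Nor does the 7-10% figure apply to every table. It does not fit Table 3.5, which is pooled, and in Table 3.6 it depends on the assumed group size.

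The practical effect may be nil. An SAE with a blank intensity has to survive data cleaning before database freeze (SAP 3.1 and 3.2). Serious events are also listed individually (Listings 10 and 11), and missing values stay blank in listings (SAP 10.7.2), so a careful reader could trace an imputed grade. That lowers the expected impact but does not make the rule right.

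**Conclusion.** The concern holds as an inconsistency between protocol and SAP, with an imputation rule that is wrong on the protocol's own scale. A blank SAE rating ranks above the worst rating an investigator can give, and seriousness is used to set severity. Tables 3.5 and 3.6 can show grades that no investigator assigned, and Table 3.21 advertises a category that cannot be filled.

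The size depends on the number of blank SAE ratings, which the documents do not allow anyone to predict and which may be zero. Each blank moves the pooled Table 3.5 by about 1.7% at 60 children, and only if the event counts as drug-related. It moves a dose-group cell in Table 3.6 by more: 7-10% under the 10-15 assumption, and about 5% to 33% across the weight bands simulated in Appendix 9.

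This rests on the protocol's three levels being what the eCRF collects, and on reading the rule's reference to a maximum-intensity summary as covering both Tables 3.5 and 3.6. Only safety reporting is affected. The primary PK analysis and the sample size are not. The SAP should be changed.

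**What to change.** If the protocol scale is what is collected:

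- In SAP 10.6.3, impute a missing intensity as severe for AEs and SAEs alike, and footnote the number imputed in each affected table.
- Show Tables 3.5 and 3.6 as mild, moderate and severe.
- Retitle Table 3.21 as severe TEAEs by preferred term, and align the matching rows of Table 3 in SAP 8.2.1.1.
- Leave seriousness and death to Tables 3.13-3.18, which already report them, so no information is lost.

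If the eCRF in fact collects a numeric grade, name the grading scale in protocol 12.3.5 and in the SAP, record the change in SAP 2.1, and add a Grade 5 row to Table 3.5.

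The first route costs only SAP wording and table shells. The second also needs a protocol text change. Neither requires new data.
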